Acute Effects of Endurance Exercise with Moderate and High Intensity on Breast Milk Composition Among Women with Overweight/Obesity

Acronym: YT

NCT number: NCT05745922

Document date: 26.02.2025

Acute effects of moderate- and high-intensity endurance exercise on breastmilk composition among women with overweight/obesity

[figure not shown]
Background

The period from conception to 2 years of age, often referred to as the “first 1000 days”, is considered the most critical for the pathophysiological disorders leading up to obesity in childhood and later life.¹ The idea that nutrition during specific windows in early life influences later health is part of a broader concept called programming, which reflects the impact of a stimulus or insult during a sensitive time-period in producing long-term changes in the structure or function of the organism.² Extensive evidence in animal models shows that nutrition during a brief critical window in early postnatal life programmes obesity, insulin resistance, dyslipidaemia, cardiovascular disease, and even lifespan.³ Also, observational data from human cohorts confirm that faster weight gain in **early** infancy is associated with a greater risk of later obesity⁴⁻⁹ Indeed, rapid weight gain in the first 3 months of life is associated with several determinants of cardiovascular disease and type 2 diabetes in early adulthood.¹⁰ The key limitation, however, of such observational studies is the lack of experimental evidence for a causal role of early nutrition in programming human health.

Identification of the molecular mechanisms contributing to rapid weight gain during infancy can guide strategies for optimal nutrition to prevent the development of childhood obesity, and thereby reduce the risk for type 2 diabetes and cardiovascular diseases later in life. During early postnatal life, the role of breastfeeding for later-life obesity is the one of the most recognised factors at play when discussing the nutritional background of childhood obesity. It has become clear during the recent decade that breastmilk composition is influenced by genetic variations and environmental factors, including geographical location, parity and mode of delivery, as well as lifestyle factors such as maternal smoking, body mass index (BMI) and diet.¹¹⁻¹⁶ One behavioural factor which has received very little attention in this regard is physical activity/exercise.

Regular exercise training is a formidable regulator of overall systemic metabolism through both acute effects driven by each exercise bout and through chronic adaptations in multiple tissues. Emerging work shows that the beneficial effects of exercise are not limited to adaptations within each tissue but from integration of inter-tissue communication by a variety of signalling molecules, hormones and cytokines collectively named ‘exerkines’.^{17,18} (Fig. 1) There are, however, little knowledge about how exercise affects human breastmilk.

Fig. 1. Exercise induce multiple molecular adaptations in the heart, adipose tissue, the pancreas, skeletal muscle, circulation, the liver, and the brain, with inter-organ crosstalk. Together these molecular factors contribute to the exercise-induced health effects, e.g., improved insulin sensitivity and reduced hyperlipidemia, which improves cardiovascular and metabolic health. There is little evidence for exercise-induced adaptations in human breastmilk (beyond increased levels of single metabolites acutely after exercise).

Human Milk Lipids

Human milk is rich in lipids, and one class of lipids that will be especially interesting are so-called “lipokines” since these lipids act as signalling molecules and can regulate inflammation and influence systemic metabolism.¹⁹⁻²¹ Some lipokines have been discovered in human milk. Yu and colleagues recently identified a breastmilk-specific lipid species (an alkylglycerol), which may protect the infant from obesity.²² The role of this signalling molecule is to impede the transformation of beige adipose tissue to lipid-storing white adipose tissue in the infant, suggesting that breastfeeding may activate adipocyte thermogenesis. Whether the abundance of this lipokine is influenced by maternal exercise is unknown. Another identified lipokine, 12,13-dihydroxy-9Z-octadecenoic acid (12,13-diHOME) was shown to regulate brown adipose tissue fuel uptake and thermogenesis in both mice and humans.²³ It was recently reported that this lipokine is present in human milk and that its abundance in breastmilk is inversely associated with infant adiposity²⁴, yet again suggesting that differences in milk lipid composition can be functionally related to early-life obesity risk. 12,13-diHOME increases fatty acid uptake in skeletal muscle and its abundance in plasma has been shown to increase in response to acute exercise.^{25,26} In the work I was involved in during my research stay in Australia, however, we found no sustained increase in 12,13-diHOME after daily exercise training ([name] et al, *in review.*), which suggest that these effects are transient. Even if recent preliminary data suggest an increase in breastmilk 12,13-diHOME in most women after acute exercise²⁴, there is no evidence for a lasting effect or, if so, whether this effect plays a causal role in early childhood obesity development.

Furthermore, recent data indicate that the relative quantity of short-chain fatty acids in human breastmilk play a role in weight gain and adiposity during infancy, with evidence for negative associations between short-chain fatty acids (butyrate, formic acid, and acetate) with measures of infant adiposity between the ages of 3 and 12 months.²⁷ These findings are supported by experimental data from animal models that identified a role for short-chain fatty acids in regulating lipid metabolism, insulin sensitivity, low-grade inflammation and body weight gain.^{28,29} Variability in fatty acid composition in breastmilk may partially explain inconsistent protective effects of breastfeeding against excessive infant adipose deposition. In line with this, exposures to different subgroups of short-chain fatty acids (the arachidonic acid/docosahexaenoic + eicosapentaenoic acid ratio) during the first 4 months of life may contribute to the way infants accumulate adipose tissue.³⁰ The relative abundance of several lipid metabolites changes acutely after exercise, in a direction opposite of what has been implicated in cardiometabolic diseases.²⁶ We discovered that exercise alters the relative abundance of metabolites involved in lipid metabolism, with a partial reversal of high-fat diet-induced increase in sphingolipid synthesis.³¹ Consequently, exercise might modify the relative abundance of lipid components also in breastmilk, and such exercise-induced effects can have implications for infant growth.

Cytokines, Adipokines and Hormones

Breastmilk contains several non-nutritive bioactive components, including hormones and cytokines. There is evidence that human milk exhibits substantial individual variation in the concentration of cytokines, adipokines and appetite-regulating hormones. Breastmilk insulin, insulin growth factor-1 (IGF-1) and leptin levels have been reported to be higher in the milk of mothers with overweight and obesity³²⁻³⁵ and different concentrations of these hormones in breastmilk has been suggested as one possible reason for high growth velocity in infants of women with poor metabolic health. Breastmilk from obese mothers has also been shown to have elevated inflammatory markers, and a pro-

inflammatory fatty acid profile that were found to be associated with infant growth and adiposity at one month of age.^{36,37} It is well established that chronic low-grade inflammation, indicated by increased pro-inflammatory cytokines such as tumour necrosis factor-alpha (TNF- α), contributes to the development and progression of metabolic disorders and non-communicable diseases such as insulin resistance, obesity and type 2 diabetes.^{38,39} Regular exercise induces suppression of TNF- α -induced insulin resistance, and this is one of the pathways explaining the protective effects of exercise against chronic diseases associated with low-grade inflammation.⁴⁰ To our knowledge, only one previous study exists on the associations between exercise and cytokines in breastmilk.⁴¹ The data from this observational study of 58 women showed that exercise was associated with elevated proinflammatory cytokines in the milk. These correlational data do, however, not provide any information about a possible causal relationship.

Human Milk Oligosaccharides (HMOs)

Human breastmilk contains a host of substances that may have mechanistic roles for metabolic health in early childhood, such as macronutrients, micronutrients, metabolic hormones, adipokines, and proinflammatory markers.^{33,42,43} In particular, human milk oligosaccharides (HMOs) have recently been linked to early infancy growth and body composition.^{14,44,45} Specifically, 2'-fucosyllactose, which is the most abundant HMO, was positively associated with infant weight gain between birth and 5 months⁴⁴, whereas 6'sialyllactose and lacto-N-neotetraose have been reported to be inversely associated with measures of infant adiposity.^{44,46} These findings indicate that certain HMOs can play a role in infant growth.

It was recently discovered that exercise training increases the abundance of the HMO 3'sialyllactose in mouse milk, and that this metabolite is a critical mediator to improve metabolic health and cardiac function in mouse offspring.⁴⁷ In the same publication, the researchers reported that 3'sialyllactose levels in human breastmilk two months postpartum were *correlated* with average steps taken per day. One main shortcoming in human breastmilk research is that almost all available data are from observational studies. As such, little is known about cause and consequences, and the associations reported may be solely due to confounding factors (such as dietary intake).

Exercise and Human Breastmilk

Exercise represents a major challenge to whole-body homeostasis and affects multiple cells, tissues, and organs in response to the increased metabolic activity of contracting skeletal muscles.¹⁷ It was recently shown that there is a dramatic shift in > 80% of annotated metabolites in the circulating metabolome in response to a single endurance-type exercise session of just 12 minutes, with beneficial alterations in metabolites representing key metabolic pathways central to obesity, insulin resistance, and inflammation.²⁶ Such alterations can help explain the broad exercise-induced benefits on cardiovascular and metabolic health.

Apart from the scarce evidence on exercise-induced adaptations in breastmilk, there is very little knowledge about how maternal exercise training affects milk composition. Women are recommended to be physically active after childbirth, but the emphasis is on maternal weight control and fitness. Current guidelines for exercise in lactating women are sparse. The most recent recommendations from the American College of Obstetricians and Gynecologists⁴⁸ merely states that “*regular aerobic exercise in lactating women has been shown to improve maternal cardiovascular fitness without affecting milk production, composition, or infant growth.*” These recommendations are based on observational studies^{49,50} and one small RCT⁵¹ from the 1990s, before today’s

advancements in various ‘omics’ technologies and the application of computational and systems biology approaches. Furthermore, no prior studies have investigated the role of exercise intensity for adaptations in breastmilk composition. There is now substantial evidence for superior effects of high-intensity exercise, as compared to moderate-intensity exercise, in a range of clinically relevant health outcomes.^{52,53}

Aim and hypotheses

The overall aim of this project is to determine the acute effect of maternal exercise on breastmilk composition. We will also compare the effects of moderate versus high intensity exercise on breastmilk composition. Our hypothesis is that: Exercise will induce substantial changes in breastmilk composition after a single endurance exercise session, with greater effects of high-intensity exercise than of moderate intensity exercise.

Methods

Participants

We will include 20-25 women with $\text{BMI} > 25 \text{ kg/m}^2$ who are exclusively breastfeeding a singleton term infant. Participants will provide a written informed consent. The assessments will be completed between 5 and 12 weeks postpartum, with the first assessment 5-9 weeks postpartum. No formal power calculation is possible for the acute study due to the exploratory nature of the research. We will continue including participants until we have complete data for all three sets of conditions for at least 20 participants. The crossover design of this study will decrease the interindividual variation in the statistical analysis. The women will serve as their own controls, which will remove any interindividual biological variance in breastmilk.

Experimental design

This will be a randomised cross-over study, in which all participants undergo three different conditions, in random order (Fig. 2):

- 1) Moderate intensity exercise; 48 min at $\sim 70\%$ of heart rate maximum
- 2) High-intensity exercise; 4 x 4 min at 90-95% of heart rate maximum
- 3) No exercise. Resting in the lab.

[figure not shown]

Fig. 2. Exercise will take place at 1000h, and breastmilk will be sampled at 0 h (immediately after exercise), + 1 h and + 4 h after exercise/no exercise. Dietary intake will be standardised on the day before and on the day of the experiment. Moderate intensity exercise (A), High intensity exercise (B) and No exercise (C) will be separated by one week and will be undertaken in random order.

Participants will walk or run on a treadmill during both exercise conditions. *Inclusion criteria:* Besteen 5+6 and 8+6 weeks postpartum at the first condition in the study, exclusively breastfeeding a term infant. *Exclusion criteria:* Known cardiovascular disease, type 1 or 2 diabetes.

Breastmilk samples (~ 25 mL) will be collected at 4 timepoints in each condition. Samples obtained after exercise and in the control condition (no exercise) will be compared to a 'baseline' sample obtained at the first breastfeeding in the morning (06-0700 h) on the same day (Fig 2). Prior to the experimental protocol, all participants will undergo a maximal effort exercise test to establish their cardiorespiratory fitness (maximum oxygen uptake) and heart rate maximum. This test will be undertaken at a separate day, at least two days prior to the first experimental condition, and takes about 30 minutes. On the same day, we will also estimate the participants' body composition using a bioimpedance scale (InBody 720), and infant weight and length. We will estimate infant body composition using biompedance (BioScan tough i8-nano).

Standardised meals

Participants will be asked to register their last meal the day before the first day of experiment, as well as the breakfast and lunch on the first day of experiment using a food diary. They will be asked to repeat the exact same meals at standardised time-points in the two following days of experiment (Fig. 2).

Questionnaires

Participants will complete the International Physical Activity Questionnaire (IPAQ) at baseline. They will also provide information on their age, ethnicity, date of delivery, the infant's birth weight, length and head circumference, and whether they are smoking or taking medications.

Breastmilk sampling

Breastmilk will be sampled by the women themselves, using an electric breast pump provided to them (Medela Symphony, Switzerland). Participants will be given a detailed instruction sheet and a link to a video for milk collection procedures. Breastmilk will be collected at the described time-points in the experimental protocol. For each mother, breastmilk will be collected from one breast (of her own

choice) for the entire study. The collected single full breast milk samples will be mixed and aliquoted into 10 x 1.8 mL sterile cryotubes and 1 x ~20 mL sterile vial, with the remaining milk for the mother to use. Samples will be frozen immediately after collection. Samples obtained after exercise training will be immediately transferred (on ice) to -80°C. The remaining samples (morning samples) will be frozen by the participants themselves at -20°C for up to 4 days before it will be transferred (cold chain) to the laboratory where it will be frozen at -80°C until analysis. The 10 x 1.8 mL aliquots will be used in the planned analyses, described below, whereas the additional 20 mL sample will be stored in a biobank for future analyses when additional funding and/or collaborations become available.

Breastmilk composition

Targeted NMR Metabolomics

Metabolic profiling of breastmilk will be analysed using nuclear magnetic resonance (NMR) spectroscopy using a Bruker Avance III Ultrashielded Plus 600 MHz spectrometer (Bruker Biospin GmbH, Germany) at NTNU MR Core Facility. After removal of residual lipids and proteins as previously described⁵⁴, each filtered sample (350 µL) will be mixed with 350 µL of 0.1 M phosphate buffer solution (pH 7.4) containing sodium 3-trimethylsilyl-(2,2,3,3-2-H3)-1-propionate (TSP) (final concentration 2 mM), and then 650 µL will be transferred into a 5 mm wide NMR tube. Metabolites will be assigned using Bruker AMIX software v.2.5 and Chenomx v.7.11 (Chenomx Inc., Canada), matching spectra to reference databases of metabolites. A mother's secretor status reflects her blood group antigens and determines her ability to synthesise certain HMOs, thus the secretor status for each individual will be determined by the high abundance (secretor) or near absence (non-secretor) of the HMO 2'-fucosyllactose in the respective milk samples with a cutoff of 100 nmol 2'FL/mL, as previously described.⁵⁵ Secretor status will be accounted for in the analysis by doing sub-group analyses of secretors vs. non-secretors.

Untargeted Global Metabolomics and Complex Lipid Panel Analysis

In parallel, untargeted metabolomics profiling panels will be applied as an unbiased screening for the relative concentrations of metabolites. These analyses will be subcontracted to Metabolon, an internationally renowned metabolomics service company who provides high sensitivity analyses of more than 1000 metabolites. The principal investigator has previous experience with Metabolon data from a diet-exercise study.³¹ Samples will be analysed using ultra-high-performance liquid chromatography-tandem mass-spectrometry (UPLC-MS/MS; positive mode), UPLC-MS/MS (negative mode) and gas chromatography-MS (GC-MS).⁵⁶ The Metabolon platform combines multiple MS methods and a laboratory information managements system with the industry's largest reference library of authenticated metabolite standards and has a suite of patented informatics and quality-control software. These features collectively allow us to overcome the 'signal-to-noise' challenges of other metabolomics platforms. In addition to the global metabolomics profiling, we will undertake Complex Lipid Panel profiling at Metabolon. Complex lipids are a diverse class of metabolites that play important roles in the development of metabolic diseases and inflammation. Because these metabolites have a diverse array of chemical structures and a high degree of isomeric overlap, lipids are exceptionally challenging to accurately identify and quantify. The Complex Lipid Panel, developed by Metabolon, is currently the best (and only) lipidomic platform to provide complete speciation data. The Complex Lipid Panel identifies up to 1,100 individual lipid species, offering unparalleled insight into the lipidome.

Cytokine and hormone profiling

We will measure a network of 27 cytokines of relevance for inflammatory status⁵⁷ (Human Cytokine Group I multiplex panel) using Luminex xMAP Technology on a Bio-Plex 200 system (Bio-Rad) at the Cellular and Molecular Imaging Core Facility (CMIC), NTNU. Since subclinical mastitis, which is a common condition, induces substantial changes in inflammatory breastmilk components⁵⁸, information of mastitis prevalence will be recorded and adjusted for in the statistical analyses. Breastmilk insulin, leptin, adiponectin will be measured by enzyme-linked immunosorbent assays (ELISA) using DS2 ELISA processing system (Dynex Technologies) at the Dept. of Circulation and Medical Imaging.

Micro-RNA sequencing

We will profile miRNA after sample preparation for extracellular vesicle enrichment of cell- and debris-free, defatted breastmilk, by precipitation (ExoQuick Exosome Precipitation Solution). Isolated RNA will be sequenced at NTNU's internal genomics facility with their standard small RNA protocol and Illumina's TruSeq SmallRNA Library Preparation Kit as per manufacturer's instructions and sequencing with a NextSeq HighOutput flow cell on a NextSeq 500 instrument (Illumina Inc.).

Biobanking and future directions

We will obtain additional milk samples for later (when funding and/or new collaborations become available; from the Research Council Norway, Horizon 2020/Horizon Europe, or other funding bodies). The samples will be stored in a research biobank specific to this project, with [name] as responsible for the biobank.

Ethics and privacy protection

Participation is voluntary and the participants can withdraw their written consent at any time. They can also request that their samples are destroyed, if they have not already been included in analyses. The project involves very little risk to the participants, except for a theoretical risk of an adverse event during exercise. Women are recommended to exercise postpartum. The knowledge gained through this project is highly needed and therefore outweighs the potential risk of exercise.

Samples may be transferred to other countries. In such instances, only the biological material (breastmilk) and ID numbers linking the participant to the sample will be transferred, and no other information about the participant.

Team, environment, and facilities

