Acute Effects of Endurance Exercise with Moderate and High Intensity on Breast Milk Composition Among Women with Overweight/Obesity

Acronym: YT

NCT number: NCT05745922

Document date: 07. September 2025

Statistical Analysis Plan

Study design: Randomized crossover study

Aim: Determine the effect of moderate-intensity continuous training and high-intensity interval training on human milk concentrations of metabolites, lipids, cytokines, hormones and miRNAs in lactating women with overweight/obesity.

Overview:

- Up to N=30 women with $\text{BMI} > 25 \text{ kg/m}^2$
- Each participant goes through three conditions in random order (six possible sequences) and has milk sampled at four time points per condition (one pre-condition and three post-condition).
- Washout period: 1 week between conditions
- The samples are analysed for a range of outcome variables within different molecular data ('omics') categories.

Conditions:

- C1: No exercise, resting in the lab
C2: Moderate-intensity continuous training
C3: High-intensity interval training

Time points:

- T1: 7 am (pre-condition)
T2: 11 am (immediately after condition)
T3: 12 am (1-hour post-condition)
T4: 15 am (4 hours post-condition)

Pre-planned outcome groups measured in human milk:

- Targeted NMR metabolomics (GCF)
Metabolomics + lipidomics profile panels (Metabolon)
Cytokines (Olink)
Hormones (insulin, ghrelin, leptin, adiponectin, IGF-1)
miRNA (GCF)

Statistical analysis plan

For each outcome category, the primary objective is to evaluate the effect of conditions C2 and C3 on the outcome variables at time points T2, T3, and T4, using condition C1 and time point T1 as references. Outcomes measured in all participants will be analysed according to the intention-to-treat principle, whereas outcomes measured only in participants who followed the protocol perfectly will be analysed according to the per-protocol principle. The decision whether to include all samples or only those from participants who complied with the protocol will depend on the costs of including the extra (non-compliant) samples for each outcome group.

We will perform the following six analysis steps for all outcome groups:

1) Data preparation (batch adjustment, log transformation, imputation)

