- If needed, the outcome data will be batch adjusted, imputed (e.g. using the R package *zCompositions*), and log transformed appropriately before analysis. Adjustments and transformations will depend on whether the data is already normally distributed, and if it is required for the method in question.
- The metabolomics data from Metabolon already comes in a log-transformed, batch-normalized version where missing values (below the detection limit) are imputed to the observed minimum for that metabolite after batch normalization. These will be used in all analyses.

2) Principal component analysis (PCA)

- We will use PCA to detect outliers and identify global structures/important features by capturing the maximum variance in the dataset, and test if the data separates according to the conditions in an unsupervised setting.
- We will identify the number of PCs that explain 95% of the variation in the data at baseline, for use in multiple testing adjustment.

3) Linear mixed model (LMM) analyses:

- We will use LMM analyses to evaluate the effects of each condition and time point on all outcome variables:
- We will analyse the effects of time and time-condition interaction as fixed effects, and participant ID as a random intercept (Eq 1). The analysis will be reference coded, with C1 (no exercise) and T1 (morning) as reference points. We will not adjust for or subtract baseline values in the model.

Eq. 1: $\text{value} \sim \text{time} + \text{time:condition} + (1|\text{id})$

- We will run the LMM analyses using e.g. the lme4 R package, and estimate p-values using the Satterthwaite method, e.g., as implemented in the lmerTests R package.
- Multiple testing correction: We will use a multiple testing corrected p-value threshold determined by dividing the alpha level (0.05) by the number of PCs explaining 95% of the variation in the outcome data at baseline.
- For variables passing the multiple testing corrected p-value cut-off, we will test for potential carry-over effects by adjusting for sequence (Eq. 2) in sensitivity analysis:

Eq. 2: response matrix ~ time + time:condition + sequence + sequence:condition + time:sequencec:condition + (1|id)

4) Repeated Measures (RM)-ASCA+

- We will use RM-ASCA+ to evaluate the overall effect of each condition and time point on each outcome data category. We will model all variables within the same data category together in a multiple-response variable analysis.

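### The protocol predicts a greater effect of high than of moderate intensity, but the SAP names no contrast between the two exercise sessions

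*Protocol*

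**What the plan says.** The protocol, under Aim and hypotheses, gives the acute effect of exercise as the overall aim and then adds a second: "We will also compare the effects of moderate versus high intensity exercise on breastmilk composition". The hypothesis that follows has a direction: "with greater effects of high-intensity exercise than of moderate intensity exercise". Under Experimental design, every woman undergoes both exercise sessions and the rest session, so the comparison can be made within women. Under Participants, no power calculation is given, "due to the exploratory nature of the research".

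The SAP labels rest C1, moderate-intensity continuous training C2 and the high-intensity session "C3: High-intensity interval training". Its primary objective is to evaluate C2 and C3 at T2, T3 and T4, "using condition C1 and time point T1 as references". For the mixed model in step 3 it says "The analysis will be reference coded, with C1 (no exercise) and T1 (morning) as reference points", and step 4 (RM-ASCA+) uses the same coding. It adds "We will not adjust for or subtract baseline values in the model". The significance threshold comes from "dividing the alpha level (0.05) by the number of PCs explaining 95% of the variation in the outcome data at baseline".

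Two other steps look across conditions. Step 2 (PCA) asks whether the data separate by condition without supervision. Step 5 (PLS-DA) maximises separation between conditions and ranks variables, with the pairs to be compared chosen in the light of the mixed-model and RM-ASCA+ results.

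**The concern.** A directional hypothesis about two sessions needs an estimate of the difference between those sessions. The SAP fixes the model, the p-value method and the threshold for each session against rest. It does not say which quantity will decide whether the high-intensity session had the greater effect, or report that quantity with an interval. The choice is left until the results are known.

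With only contrasts against rest on the page, a reader may judge intensity by which session crosses the threshold. The difference between a result that passes and one that does not is not itself a tested difference, and its error rate is not held at the nominal level when the two sessions have equal effects. A direct contrast holds that rate and also gives the size of the difference.

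**Working it through.** The documents give no effect size, SD or power figure to reproduce. The checks below use residual SD units (s), complete balanced data, the random-intercept model of Eq. 1 and normal approximations. The 20 women are the protocol's minimum with complete data, and 30 is the SAP's maximum. The number of PCs is not given; 20 is an assumption used to show a corrected threshold of 0.05/20 = 0.0025.

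**1. What Eq. 1 reports.** With C1 and T1 as references, Eq. 1 expands to 12 coefficients:
- one intercept;
- three time effects under rest;
- eight condition terms (C2 and C3 at each of T1 to T4), each a difference from C1 at that time.

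None is C3 minus C2.

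**2. Is the contrast available from the same fit?** Yes, as the C3 term minus the C2 term at each time. With n = 20:
- Var(C2−C1) = Var(C3−C1) = 2s²/20 = 0.10s².
- Their covariance, through the shared rest session, is s²/20 = 0.05s², so the correlation is 0.05/0.10 = 0.5.
- Var(C3−C2) = 0.10s² + 0.10s² − 2 × 0.05s² = 0.10s², the same precision as a contrast with rest.

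**3. Detectable difference, 80% power.** The formula is (z for two-sided alpha + 0.842) × s√(2/n).

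| | n = 20 (SE 0.316s) | n = 30 (SE 0.258s) |
|---|---|---|
| alpha 0.05 (z = 1.960) | 0.89s | 0.72s |
| alpha 0.0025 (z = 3.023) | 1.22s | 1.00s |

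These are for the difference at a given time point, since Eq. 1 does not subtract baseline. As a difference in change from T1, the SE is s√(4/n), and at alpha 0.05 the figures become 1.25s and 1.02s.

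**4. Illustration of a pass/fail reading.** The SAP does not state this reading. Suppose the sessions are truly equal and one looks only at which passes against rest. The chance that C3 passes and C2 does not, from a bivariate normal with correlation 0.5, is:
- about 11% when each contrast has 20% or 80% power, and about 17% at 50% power; at fixed power these hardly change with the threshold;
- with no effect of either session, about 4% at alpha 0.05 and about 0.2% at 0.0025.

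The direct test errs in that direction in 0.05/2 = 2.5% at alpha 0.05, and in 0.0025/2 = 0.125% at 0.0025, whatever the common effect.

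**5. Added multiplicity.** Post-session tests per variable rise from 2 × 3 = 6 to 3 × 3 = 9. With no effects, the chance of at least one false pass per variable rises from about 25% to about 32% at alpha 0.05, and from about 1.4% to about 2.1% at 0.0025 (simulation).

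**The case against.** The strongest reply is that reference coding is only a parameterisation. Eq. 1 already contains the C3−C2 difference, and any analyst can extract it. This stands, and it limits the point. It would be wrong to infer that the models or the design cannot answer the intensity question. What is missing is a named contrast, with its interval and threshold, fixed before the results are seen.

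A second reply is that all three conditions are examined together in PCA, RM-ASCA+ and PLS-DA. They are, but PCA and PLS-DA show separation and variable importance, not a signed difference with an interval. The PLS-DA pairs depend on earlier results, so a C3 versus C2 comparison is not guaranteed. RM-ASCA+ has bootstrap intervals, but its stated reference is again rest.

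A third reply is that the error rates in step 4 of the working describe a rule the SAP does not contain. That is correct. A reader might infer that the trial plans to judge intensity by pass/fail; the documents neither say so nor exclude it, and the figures only illustrate why the contrast should be named. Nor is pass/fail always the less sensitive reading: with true effects of 0.5s and 1.0s, 20 women and alpha 0.05, it shows only C3 passing in 54% of simulated runs, while the direct test passes in 35%. The case against it is its uncontrolled error rate.

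Finally, the comparison is a second aim in a study without a power calculation, which the protocol describes as exploratory. This stands and keeps the point modest.

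**Conclusion.** The point holds as an omission in specification. The protocol states an intensity comparison with a predicted direction, and the SAP, followed exactly, produces no estimate of it. Nothing in the documents says the aim was dropped. The primary objective's contrasts with rest are not affected by this point, and the data and planned model already support the missing contrast with the same precision as a contrast with rest.

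That the contrast is absent rests on the text alone. The numerical sizes rest on homoscedastic residuals, a random intercept, complete balanced data and, for the corrected threshold, an assumed 20 PCs. Under those assumptions the trial can detect only fairly large intensity differences: about 0.7 to 0.9 residual SDs uncorrected and 1.0 to 1.2 corrected. An interval is therefore more informative than a verdict of significant or not. This is a cheap improvement to the plan.

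**What to change.** In SAP step 3, add that for every outcome variable C3 minus C2 will be estimated at T2, T3 and T4 from the same Eq. 1 fit, with a 95% CI and Satterthwaite p-value, judged at the PC-corrected threshold. In step 4, report the C3 minus C2 effect with its bootstrap interval. Show these beside the C2−C1 and C3−C1 estimates and CIs, so that the direction of each session's effect is visible. State that passing against rest for one session and not the other is not evidence of a difference between sessions.

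Do not add a label based on the signs of the raw estimates. With a correlation of 0.5, two estimates with no true effect have opposite signs with probability arccos(0.5)/π = 1/3. A label such as 'differing in direction' would then attach to a third of null variables at each time point.

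The cost is three linear contrasts per variable and a few sentences, with no new visits, samples or assays. The downsides are the extra multiplicity, which dividing by PCs does not count, and the limited precision shown above. Both should be acknowledged in the SAP.
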